5.5.1. Thrombin Generation

Thrombin generation will be measured from plasma samples to assess the anticoagulant effect of FXa inhibitors. Tissue factor-dependent thrombin generation will be performed at a central laboratory. Five parameters related to thrombin generation are measured as follows: endogenous thrombin potential (ETP; the primary measure), peak height, time to peak height, laboratory time, and velocity index. Thrombin generation parameters will be obtained at baseline and at 1 and 12 hours post-randomization.

Descriptive statistics for change and percent change from baseline will be provided for each parameter by treatment group and by visit.

The difference between the 2 treatment groups in ETP change from baseline will be evaluated using an MMRM, adjusting baseline ETP value. The least-squares (LS) mean difference in

Page 22 of 52 Alexion Confidential change from baseline and its 95% CI will be reported at 1 and 12 hours post-randomization visit, as well as across all post-randomization visits through 12 hours.

The MMRM model that analyzes ETP will contain the following fixed-effect terms:

- Time from symptom onset to the baseline imaging scan (< 180 minutes versus ≥ 180 minutes)
- Treatment group (and examet versus UC)
- Visit (baseline, 1 and 12 hours post-randomization)
- Treatment-by-visit interaction

Participants will be treated as a random effect to take account of the correlation of the measurements within the same participant. An unstructured covariance matrix will be used to model within-participant variances. This model imposes no assumptions on mean trend and correlation structure and is considered robust. Denominator degrees of freedom will be estimated using the Kenward-Roger approximation. If there is a convergence problem due to the unstructured covariance matrix, the unstructured covariance matrix will be replaced by other covariance matrices in the following order until convergence is met: autoregressive of order 1 [AR(1)], Toeplitz, and compound symmetry.

By-participant listings of thrombin generation parameters will be provided.

5.5.2. Neurologic Deterioration at 12 and 24 Hours

The proportion of participants with neurologic deterioration at 12 hours, defined as the number of participants with a \geq 7-point increase from baseline to 12 hours in NIHSS, will be tabulated. Neurologic deterioration at 24 hours is deteriorations meeting at least 1 of the following 2 criteria.

- An increase in the NIHSS score \geq 4 at 24 hours post-randomization compared with baseline.
- A decrease in the Glasgow Coma Scale (GCS) score ≥ 2 at 24 hours post-randomization compared with baseline.

A CMH test stratified by time from symptom onset to the baseline imaging scan will be used to compare and exanet and UC in the proportion of neurologic deterioration at 12 and at 24 hours post-randomization, respectively. The difference in the proportion and its 95% CI will be reported.

By-participant listings of neurologic deterioration at 12 and 24 hours will be provided.

5.5.3. Modified Rankin Scale

The modified Rankin Scale (mRS) score will be obtained at baseline (premorbid) and at 30 days post-randomization or at the Early Termination Visit. If the baseline mRS is unavailable during Screening, the mRS can be collected from the participant, relative, caregiver, or legally authorized representative at a post-randomization time point as long as the mRS reflects the participant's premorbid (ie, pre-ICrH) neurologic status. The premorbid mRS should reflect the

participant's neurologic status prior to acute illness. Tabulation of mRS scores at baseline and Day 30 will be provided by treatment group.

mRS at 30 days post-randomization will be dichotomized into 1 (functional independence: scores of 0, 1, 2, and 3) and 0 (functional dependence: scores of 4 and 5; death: score of 6). A logistic regression model will be used to analyze mRS at Day 30, adjusting for baseline mRS, time from symptom onset to the baseline imaging scan, and treatment group. The odds ratio for the treatment effect with 95% CI will be reported.

Summaries of shifts in functional independence from baseline to Day 30 will also be provided by treatment group.

By-participant listings of mRS will be provided.

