variable (proportion of neurological deterioration at 24 hours) will be analyzed using a stratified CMH test.
The individual thrombin generation and mRS score (ordinal, dichotomous, and utility-weighted analyses) will be analyzed as well.
For additional efficacy analysis refer to the Statistical Analysis Plan.

LIST OF ABBREVIATIONS AND TERMS

Abbreviation	Definition
AE	Adverse Event
AESI	AEs of Special Interest
ANCOVA	Analysis of Covariance
Andexanet	Andexanet Alfa
CFR	Code of Federal Regulations
CI	Confidence Interval
CIOMS	Council for International Organizations of Medical Sciences
СМН	Cochran-Mantel Haenszel
COVID	Coronavirus Disease 2019
СР	Conditional Power
CRF	Case Report Form
СТ	Computed Tomography
cTn	cardiac Troponin
CV	Cardiovascular
DBP	Diastolic Blood Pressure
DIC	Disseminated Intravascular Coagulation
DSMB	Data Safety Monitoring Board
DVT	Deep Vein Thrombosis
EAC	Endpoint Adjudication Committee
eCRF	Electronic Case Report Form
ECG	Electrocardiogram
ED	Emergency Department
EDC	Electronic Data Capture
EQ-5D	EuroQol-5 Dimension
ETP	Endogenous Thrombin Potential
FDA	(US) Food and Drug Administration
FFP	Fresh Frozen Plasma
FX	Factor X
FXa	Factor Xa
GCP	Good Clinical Practice
GCS	Glasgow Coma Scale
GDPR	General Data Protection Regulation
HIPAA	Health Insurance Portability and Accountability Act
IB	Investigator's Brochure
ICF	Informed Consent Form
ICH	International Council for Harmonisation of Technical Requirements for Pharmaceuticals for Human Use

Abbreviation	Definition
ICrH	Intracranial Hemorrhage
IEC	Independent Ethics Committee
INR	International Normalized Ratio
IRB	Institutional Review Board
ITT	Intent-to-Treat
IV	Intravenous
LAR	Legally Authorized Representative
LBBB	left bundle branch block
MedDRA	Medical Dictionary for Regulatory Activities
MI	Myocardial Infarction
MRI	Magnetic Resonance Imaging
mRS	Modified Rankin Scale
NIHSS	National Institutes of Health Stroke Scale
NSAID	Non-Steroidal Anti-Inflammatory Drug
PaO ₂ /FIO ₂	Arterial oxygen partial pressure/fractional inspired oxygen
PCC	Prothrombin Complex Concentrate
PD	Pharmacodynamic
PE	Pulmonary Embolism
РК	Pharmacokinetic
РР	Per Protocol
PRBC	Packed Red Blood Cell
rfVIIa	Recombinant factor VIIa
SAE	Serious Adverse Event
SAP	Statistical Analysis Plan
SBP	Systolic Blood Pressure
SSR	Sample Size Re-estimation
SUSAR	Suspected Unexpected Serious Adverse Reaction
ТЕ	Thrombotic Event
TEAE	Treatment-Emergent Adverse Event
TFPI	Tissue Factor Pathway Inhibitor
TIA	Transient Ischemic Attack

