2.0 STUDY OBJECTIVES

Table 1 summarizes the objectives and endpoints of this study in oral FXa inhibitor-treated patients with acute intracerebral hemorrhage.

Table 1: Study 18-513: Objectives and Endpoints		
Objectives	Endpoints	
PRIMARY EFFICACY		
• Evaluate the effect of and examet versus usual care on the rate of effective hemostasis.	• Effective hemostasis 12 hours post-randomization as determined by the blinded EAC.	
SECONDARY EFFICACY		
• Evaluate the effect of and examet versus usual care on anti-fXa activity.	• Percent change from baseline to nadir in anti-fXa activity during the first 2 hours post-randomization.	
ADDITIONAL EFFICACY		
• Evaluate the effect of andexanet versus usual care on thrombin generation.	• Change from baseline in thrombin generation parameters (with ETP as the primary measure), obtained at 1 and 12 hours post-randomization.	
Evaluate the effect of andexanet versus usual care on neurologic function.	 Proportion of neurologic deterioration, as defined by an NIHSS score increase ≥ 4 or a GCS score decrease ≥ 2 at 24 hours post-randomization versus baseline. 	
	• Change from baseline in mRS score at 30 days post-randomization.	
	• Change from baseline in NIHSS score obtained at 2, 3, 6, 12, 24, and 72 hours post-randomization.	
	• Change from baseline GCS score obtained at 2, 3, 6, 12, 24, and 72 hours post-randomization.	
	• Proportion of patients with a ≥ 7-point increase from baseline in NIHSS score at 12 hours post-randomization.	
	• Hemostatic efficacy evaluated using only imaging parameters.	
	• Proportion of patients using rescue therapy between 3 and 12 hours post-randomization.	
• Assess the relationship between anti-fXa activity and the achievement of hemostatic efficacy.	• Correlation analysis between anti-fXa activity and the achievement of hemostatic efficacy.	
• Evaluate the effect of andexanet versus usual care on health-related quality of life.	• Health-related quality of life as assessed by the EQ-5D questionnaire at 30 days post-randomization.	
	• UW-mRS score at 30 days post-randomization.	

Table 1: Study 18-513: Objectives and Endpoints		
Objectives	Endpoints	
SAFETY		
• Evaluate the occurrence of TEs at 30 days after randomization.	• Occurrence of TEs, confirmed by adjudication, through 30 days post-randomization.	
• Evaluate in-hospital and 30-day mortality (all-cause, CV, and bleeding).	• In-hospital mortality (during index hospitalization; all-cause, CV, and bleeding).	

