10.5.4.4. Additional Efficacy Analyses

Thrombin generation parameters (with ETP as the primary measure) will be obtained at baseline, 1 hour, and 12 hours post-randomization. The difference between the two treatment groups will be evaluated using a mixed effects model similar to the model described below for the analysis of the NIHSS and GCS scores.

The change from baseline in NIHSS and change from baseline in GCS will be analyzed using a mixed linear model with covariates, including the baseline measurement and the following fixed effect terms:

- Stratification factor of time from symptom onset to baseline imaging scan (< 180 minutes vs. ≥ 180 minutes)
- Treatment arm (usual care/andexanet)
- Time (measurements at 2, 3, 6, 12, 24, and 72 hours post-randomization)
- Treatment-by-time interaction

Patients will be treated as a random effect to take account of the correlation of the measurements within the same patient.

Neurologic deterioration at 24 hours defines deterioration as meeting at least one of the following 2 criteria:

- An increase in NIHSS score ≥ 4 at 24 hours post-randomization compared with baseline;
- A decrease in GCS score ≥ 2 at 24 hours post-randomization compared with baseline.

The CMH test stratified by time from symptom onset to baseline imaging scan will be used to test the treatment difference in the proportion of neurologic deterioration at 24 hours.

Change from baseline in mRS scores at 30 days post-randomization will be analyzed using a proportional odds model adjusted for baseline mRS, the stratification factor, treatment arm, and potentially other clinical factors.

The relationship between anti-fXa activity and the achievement of clinical events such as hemostatic efficacy and mortality will be evaluated. A logistic regression adjusted for potentially other clinical factors, the stratification factor in the primary efficacy analysis, and treatment arm will be used to evaluate the relationship.

Further details of these analyses will be provided in the SAP.

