5.11.	Handling of Laboratory Samples Out of Stability	33
6. S	UPPORTING DOCUMENTATION	34
6.1.	Appendix 1: Technical Specifications for Derived Variables	34
6.2.	Appendix 2: Study and Participant Characteristics	44
6.2.1.	Protocol Deviations	44
6.2.2.	Demographics and Disease Characteristics	44
6.2.2.1.	Demographics and Disease Characteristics (Bleeding)	44
6.2.2.2.	Medical/Surgical History and Baseline Physical Examination	46
6.2.3.	Prior and Concomitant Medications	46
6.3.	Appendix 3: Instrument Scoring Details	46
6.3.1.	Glasgow Coma Scale	46

6.3.2.	Utility-Weighted mRS	46
6.3.3.	EQ-5D-5L Health State Index Score Calculations	47
6.4.	Appendix 4: Additional Details on Statistical Methods	
6.4.1.	COVID-19 Vaccine Risk Assessment	
6.4.1.1.	Vaccination	
6.4.1.2.	Potential Risks and Mitigation Measures	
6.4.1.3.	Reason for Not Collecting COVID-19 Information	
6.5.	Appendix 5: Changes to Protocol-Planned Analyses	
6.6.	Appendix 6: List of Abbreviations	
7.	REFERENCES	

LIST OF TABLES

Table 1:	Objectives and Endpoints	8
Table 2:	Analyses Sets	.15
Table 3:	Attributes of Primary (Composite) Estimand	.18
Table 4:	AEs and SAEs	.27
Table 5:	Clinically Significant Laboratory Criteria	.43
Table 6:	Clinically Significant Vital Sign Criteria	.43
Table 7:	EQ-5D-5L US cTTO Value Set	.47

VERSION HISTORY

This statistical analysis plan (SAP) for Study 18-513 is based on Protocol Version 3.0, dated 05 Dec 2022.

SAP Version	Version Date	Change	Rationale
0.2	07 Jun 2022	Not applicable	Original version
1.0	30 Nov 2022	 Updated primary efficacy analysis to using one stratification factor Updated sensitivity analyses for the primary endpoint Updated the analysis for secondary endpoint Updated analyses for correlation between effective hemostasis and anti-fXa activity Updated subgroup analysis Updated language in the section for interim analysis for better clarification Updated definition for the per protocol set 	Changes are made to align with the Protocol Amendment V3 and to incorporate comments from regulatory agency review
1.1	17 Apr 2023	 Added clarification of two data cutoff (DCO) points Added definition of screened set 	Changes are made to clarify the data used for the interim analysis, and the final analysis; and to differentiate the screened participants from the enrolled participants.

APPROVAL SIGNATURES

		20-Apr-2023 11:02 EDT
	, Alexion	Date dd Mmm yyyy
		20-Apr-2023 10:53 EDT
	, Alexion	Date dd Mmm yyyy
		21-apr-2023 12:43 IST
AstraZeneca	, ,	Date dd Mmm yyyy

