1.1. Objectives and Endpoints

The overall objective of the study is to gain direct insights regarding the efficacy and safety of andexanet in Factor Xa (FXa)-anticoagulated participants with acute intracranial hemorrhage (ICrH).

The objectives, endpoints, and analysis population for each endpoint are summarized in Table 1. Attributes of the estimates for the primary efficacy analyses are found in Section 5.3.1.

Objectives	E	ndpoints
Primary Efficacy		
• Evaluate the effect of and versus usual care on the ra effective hemostasis		Effective (good and excellent) hemostasis 12 hours post-randomization as determined by the blinded EAC
Secondary Efficacy		
• Evaluate the effect of and versus usual care on anti-factivity		Percent change from baseline to nadir in anti-fXa activity during the first 2 hours post-randomization
Additional Efficacy		
• Evaluate the effect of and versus usual care on throm generation		Change from baseline in thrombin generation parameters (with ETP as the primary measure), obtained at 1 and 12 hours post-randomization
• Evaluate the effect of and versus usual care on neuro function		Proportion of neurologic deterioration, as defined by an NIHSS score increase ≥ 4 or a GCS score decrease ≥ 2 at 24 hours post-randomization versus baseline.
	•	Change from baseline in the mRS score at 30 days post-randomization.
	•	Change from baseline in the NIHSS score obtained at 2, 3, 6, 12, 24, and 72 hours post-randomization

Table 1:Objectives and Endpoints

Table 1:Object	tives and	Endpoints
----------------	-----------	-----------

Ob	jectives	En	dpoints
		•	Change from baseline in the GCS score obtained at 2, 3, 6, 12, 24, and 72 hours post-randomization
		•	Proportion of participants with $a \ge 7$ -point increase from baseline in the NIHSS score at 12 hours post-randomization
		•	Hemostatic efficacy evaluated using only imaging parameters
		•	Proportion of participants using rescue therapy and/or procedures between 3 and 12 hours post-randomization
•	Assess the relationship between anti-fXa activity and the achievement of effective hemostasis	•	Correlation analysis between anti-fXa activity and the achievement of effective hemostasis
•	• Evaluate the effect of and examet versus usual care on health-related		Health-related quality of life as assessed by the EQ-5D questionnaire at 30 days post-randomization
	quality of life	•	UW-mRS score at 30 days post-randomization
Sa	fety		

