5. STATISTICAL ANALYSIS

5.1. General Considerations

During the conduct of the study, the Sponsor and Investigators will be blinded to the aggregated efficacy and safety summaries. In addition, all unblinded analyses that are required to support the DSMB will be performed by an independent unblinded DSMB statistician. These analyses will be performed under the direction of the DSMB according to the analyses described the DSMB Charter. The results of these unblinded analyses will not be available to the Sponsor or Investigators until after database lock.

The safety interim analyses will follow the same procedures as the efficacy interim analysis (see Protocol Section 10.7), with the Sponsor remaining blinded to the results of these analyses unless the DSMB recommends stopping the study early.

Once the study is complete and the final database lock is performed, the study will be fully unblinded and the final analyses will be performed.

All efficacy and safety endpoint parameters will be summarized descriptively.

For continuous variables, the number of observations, mean, median, SD, first quartile, third quartile, interquartile range, and minimum and maximum values will be presented. For categorical variables, unless specified otherwise, counts and percentages will be based on the number of participants with nonmissing values in each treatment group and total. Inferential statistics will be presented only when specified.

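### The SAP omits the protocol's ordinal analysis of 30-day mRS without declaring it, and plans no between-arm estimate for the utility-weighted mRS endpoint

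*SAP*

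**What the plan says.** **mRS.** Protocol 10.5.4.4: "Change from baseline in mRS scores at 30 days post-randomization will be analyzed using a proportional odds model adjusted for baseline mRS", with the stratification factor and treatment arm also in the model. The Statistical Analysis part of the Synopsis adds: "mRS score (ordinal, dichotomous, and utility-weighted analyses) will be analyzed as well". SAP Table 1 keeps the endpoint as "Change from baseline in the mRS score at 30 days post-randomization". SAP 5.5.3 plans four things:
- a tabulation of mRS at baseline and Day 30 by arm;
- the split "mRS at 30 days post-randomization will be dichotomized into 1 (functional independence: scores of 0, 1, 2, and 3) and 0" (0 covers scores 4 to 6);
- one logistic regression on that split;
- descriptive shifts of the dichotomised state.

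No ordinal model appears anywhere in the SAP. Appendix 5 declares one change, the enrolled-set definition.

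**uw-mRS.** SAP Table 1 lists "UW-mRS score at 30 days post-randomization". Protocol Table 1 places this endpoint under the objective "Evaluate the effect of andexanet versus usual care on health-related quality of life". SAP 5.5.9 gives the mean and SD of utilities at each mRS score, by arm. SAP 6.3.2 says the weights will be used in analyses but names none. SAP 5.1 states: "Inferential statistics will be presented only when specified".

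**The concern.** A statistician who follows the SAP as written will not produce an adjusted common odds ratio that the protocol names, and nothing records that this was intended. If the ordinal result is wanted later, it will look post hoc.

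The uw-mRS has a listed comparative objective but no planned output that compares it. Conditioning on the mRS score removes the shift in scores that the uw-mRS is meant to value. Since inferential statistics appear only where specified, no comparison arises by default.

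**Working it through.** No document figure is in dispute, so the main check is textual.

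| Item | Protocol | SAP |
|---|---|---|
| Ordinal mRS model | Synopsis; 10.5.4.4 | absent |
| Dichotomous mRS model | Synopsis | 5.5.3 |
| Utility-weighted analysis | Synopsis | 5.5.9, within-score means only |
| Change declared | n/a | none in Appendix 5 |

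**Precision of the two mRS models (illustrative).** The documents give no mRS distribution or effect. Assumed usual-care mRS 0 to 6 (%):
- A: 2/4/7/12/22/18/35
- B: 3/6/10/14/21/16/30
- C: 4/8/12/16/20/15/25
- D: 6/12/15/17/18/12/20

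Assume a common OR of 1.4, no covariates, and n = 450 per arm (N = 900).

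- Ordinal: V = n·n·N / [3(N+1)²] × (1 − Σ m³), where m is the mean share in each category over the arms; SE = 1/√V.
- Dichotomous: variance = Σ over arms of 1/[n·p(1−p)], where p is the share at 0-3.

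Distribution A: usual care p = 0.25. Andexanet odds are 0.3333 × 1.4 = 0.4667, so p = 0.318.
- Dichotomous variance = 1/(450×0.25×0.75) + 1/(450×0.318×0.682) = 0.0221; SE 0.149; 95% CI 1.05 to 1.87.
- Ordinal V = 74.8 × (1 − 0.051) = 71.0; SE 0.119; 95% CI 1.11 to 1.77.
- Ratio of SEs 1.25.

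B gives a ratio of 1.18, and C and D give 1.15. At 225 per arm (the interim cutoff) the range is again 1.15 to 1.25.

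**When odds are not proportional.** In simulation (40,000 trials per setting, 450 per arm, OR 1.5 at the 3/4 cut, two-sided 0.05), the share of trials with p < 0.05 was:
- all benefit is a move from 4 to 3: 12-16% ordinal, 79-85% dichotomous;
- patients spread proportionally within 0-3 and 4-6: 61-76% ordinal, 79-86% dichotomous.

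**uw-mRS (illustrative).** Two assumed weight sets for mRS 0 to 5 were used (.95/.88/.75/.60/.30/0 and .90/.80/.70/.50/.25/−.10), with death at 0. If patients at the same score have the same utility in both arms, the SAP 5.5.9 table shows no gap whatever the mRS shift. The uw-mRS mean difference is −0.07 to −0.04 at OR 0.71, 0 at OR 1.0, and +0.05 to +0.07 at OR 1.4. The table and the endpoint therefore measure different things. Treating the weights as known, the 95% CI half-width at OR 1.4 would be about 0.04-0.05 at 450 per arm and 0.055-0.065 at 225 per arm.

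**The case against.** **The protocol defers to the SAP.** The Synopsis sends the reader there for additional efficacy analyses, 10.5.4.4 does so for further details, and Section 10.0 calls itself a summary. It would be wrong to infer that nothing points to the governing document; the pointers favour the SAP. But supplying details of a named model is not removing it, and Appendix 5 is the place to record a removal.

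**The dichotomous model is not a departure.** The Synopsis lists it. A reader might also infer that it is the worse choice. The simulations above do not support that.

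**A Day-30 ordinal model is not literally the protocol's.** The protocol applies its model to change from baseline, so the intervals above do not price that exact analysis. This stands, and the wording needs aligning whichever model is kept.

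**The version history proves little.** A reader might take "Changes are made to align with the Protocol Amendment V3 and to incorporate comments from regulatory agency review" as a claim that every section now matches the protocol. It is the rationale for a list of named changes, none about mRS.

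**The EQ-5D comparison covers part of the uw-mRS.** SAP 5.5.8 plans a between-arm difference with 95% CI for the EQ-5D-5L index, so the quality-of-life objective as a whole is not without a comparison. With complete data, pooled weights and deaths at 0, the index difference equals the uw-mRS difference plus the between-arm gap in utilities at equal scores. With the first weight set and OR 1.4, both are 0.055-0.066 at zero gap. With a gap of ±0.05, the index difference ranges over 0.019-0.108 and the uw-mRS difference over 0.053-0.067. The overlap is real but partial, and SAP 5.5.8 does not say whether deaths enter the index at 0. A crude uw-mRS point estimate could also be built by hand from the planned tables, but without a planned interval.

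**Conclusion.** The point holds in two parts. The SAP omits a protocol-named ordinal analysis of 30-day mRS and does not declare the omission. It also plans no between-arm estimate or interval for the uw-mRS. Both rest on the current text of the two documents and are firm.

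The sizes are illustrative because every distribution, weight and effect is assumed: a standard error 15-25% larger for the dichotomous log odds ratio under proportional odds, with the ranking able to reverse for other effect shapes. That supports reporting both models, not preferring one.

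The consequence is limited. The full mRS distribution by arm, an adjusted dichotomous odds ratio, the mortality model and the EQ-5D comparisons all remain. A reader might infer a threat to the main result, but SAP 5.1.1 confines formal testing to the primary and secondary endpoints, so those conclusions, alpha and sample size do not change. It belongs at the low end of what should be fixed.

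**What to change.** 1. In SAP 5.5.3, add a proportional odds model of Day-30 mRS (0 to 6), adjusted for baseline mRS, time stratum and arm, beside the dichotomous model. Align the change-from-baseline wording in Protocol 10.5.4.4 and SAP Table 1 with it. If the model is not added, declare and justify the omission in Appendix 5.
2. In SAP 5.5.9, give each patient the pooled weight for his or her Day-30 mRS, with death at 0 as in SAP 6.3.2. Report the between-arm mean difference with 95% CI, as SAP 5.5.8 does for the EQ-5D index. A bootstrap interval is an option, because the weights come from the same patients. In the same edit, let the weights in SAP 6.3.2 cover mRS 0 to 5. It now says 1 to 5, probably a slip, since SAP 6.1 covers each category.

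Cost: SAP wording and two additional models on data already collected. Nothing changes in the primary test, alpha or sample size.

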APPENDIX D. MODIFIED RANKIN SCALE (MRS)

Score	Description
0	No symptoms at all
1	No significant disability despite symptoms; able to carry out all usual duties and activities
2	Slight disability; unable to carry out all previous activities, but able to look after own affairs without assistance
3	Moderate disability; requiring some help, but able to walk without assistance
4	Moderately severe disability; unable to walk without assistance and unable to attend to own bodily needs without assistance
5	Severe disability; bedridden, incontinent, and requiring constant nursing care and attention
6	Dead

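### SAP 5.5.3 labels Day-30 mRS 0–3 as functional independence, although the protocol's own scale describes score 3 as needing some help

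*SAP*

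**What the plan says.** SAP 5.5.3 (Modified Rankin Scale) creates one binary variable from the Day-30 score. The favourable category is "mRS at 30 days post-randomization will be dichotomized into 1 (functional independence: scores of 0, 1, 2, and 3"; the other is "0 (functional dependence: scores of 4 and 5; death: score of 6". The variable feeds a model: "A logistic regression model will be used to analyze mRS at Day 30, adjusting for baseline mRS", with the symptom-onset-to-scan stratum and treatment group as the other terms, and an odds ratio with 95% CI reported. The same section adds: "Summaries of shifts in functional independence from baseline to Day 30 will also be provided by treatment group". It also promises the raw distribution, "Tabulation of mRS scores at baseline and Day 30 will be provided by treatment group", and by-participant listings.

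Protocol Appendix D is the trial's copy of the scale. Score 2 reads "Slight disability; unable to carry out all previous activities, but able to look after own affairs without assistance". Score 3 reads "Moderate disability; requiring some help, but able to walk without assistance".

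The protocol synopsis names a dichotomous mRS analysis among others but gives no cut-point.

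**The concern.** The SAP's name for category 1 and the scale's description of score 3 do not agree. What score 3 shares with scores 0–2 is walking unaided. What it does not share is managing without help, which is what a reader will take functional independence to mean.

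Two outputs carry the label. The first is the odds ratio, which would naturally be written up as an effect of andexanet on functional independence. It is the only mRS treatment comparison that SAP 5.5.3 models; SAP 5.5.9 gives only means and SDs for the utility-weighted score. The second is the baseline-to-Day-30 shift summary. Baseline mRS is premorbid status, so this is the output a reader would consult to see how many patients lost their independence.

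What is at stake is the wording of a functional conclusion, not a confirmatory decision.

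**Working it through.** The plan states no mRS rate, so there is no figure to reproduce. The check compares definitions and then applies a short identity.

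**1. Score by score.** Descriptions are paraphrased from Protocol Appendix D; the SAP flag is from SAP 5.5.3.

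| mRS | Appendix D, in short | SAP flag | Flag if independence = 0–2 |
|---|---|---|---|
| 0 | no symptoms | 1 | 1 |
| 1 | symptoms, but usual activities done | 1 | 1 |
| 2 | manages own affairs unaided | 1 | 1 |
| 3 | needs some help; walks unaided | 1 | 0 |
| 4 | can neither walk nor see to bodily needs unaided | 0 | 0 |
| 5 | bedridden, constant nursing care | 0 | 0 |
| 6 | dead | 0 | 0 |

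The two definitions differ at score 3 only.

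**2. Size within an arm.** P(0–3) − P(0–2) = P(3). The documents do not give P(3). Assume 5% to 25%, and take the planned 450 patients per arm (Protocol 10.3) as the denominator:

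- P(3) = 5%: gap of 5 percentage points; 0.05 × 450 = 22.5, about 23 patients.
- P(3) = 25%: gap of 25 percentage points; 0.25 × 450 = 112.5, about 113 patients.

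**3. Between arms.** Write D(·) for the andexanet-minus-usual-care difference in a proportion. Then D(0–3) = D(0–2) + D(3). If treatment only moves patients from 4 to 3, D(0–3) is positive and D(0–2) is zero. If it only moves patients from 3 to 2, D(0–2) is positive and D(0–3) is zero. So a result for one cut is not a result for the other. The documents do not allow the direction or size of any difference to be predicted.

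**4. Shift summary.** Assume the Day-30 cut is also applied to premorbid mRS. The SAP does not say so; it defines the cut for Day 30 only.

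| Premorbid → Day 30 | SAP 0–3 cut | 0–2 cut |
|---|---|---|
| 0 → 3 | 1 → 1, no change | 1 → 0, loss |
| 1 → 3 | 1 → 1, no change | 1 → 0, loss |
| 2 → 3 | 1 → 1, no change | 1 → 0, loss |
| 3 → 4 | 1 → 0, loss | 0 → 0, no change |

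Under that assumption, a patient who needed no help before the bleed and needs some at Day 30 appears as unchanged. The last row shows that the 0–3 cut picks up a different loss, that of walking and self-care, which is also worth knowing.

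**The case against.** The strongest reply is that the label is defined where it is used. The scores are listed inside it, the rule is prespecified, and it applies identically to both arms. That stands. A reader might infer that the odds ratio is biased or invalid; the documents do not support this. It is a sound estimate for 0–3 versus 4–6.

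Appendix D also never uses the words independent or dependent, and its score 4 is the first grade unable to walk or attend to bodily needs unaided, so the 3/4 boundary has a clear meaning. That stands too: no document sets independence at 0–2. The 0–2 reading rests on the contrast between "unable to carry out all previous activities, but able to look after own affairs without assistance" at score 2 and the need for some help at score 3. That contrast is enough to make the present label misleading. It is not enough to say that the scale formally classes score 3 as dependent.

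Three further inferences are tempting and go too far.

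- *That this is the trial's only Day-30 functional comparison.* SAP 5.5.8 compares the arms on each EQ-5D dimension by stratified CMH test and on the index by ANCOVA. Protocol 10.5.4.4 also plans a proportional odds model for change in mRS. SAP 5.5.3 does not carry it and SAP Appendix 5 does not list its removal, but that is a separate matter.
- *That the information is lost.* The score tabulation gives the 0–2 proportion by arm, and the listings allow individual transitions to be traced. Only the shift summary would conceal them, and only if the cut is also used at baseline.
- *That a reported independence rate is inflated by a known amount.* SAP 5.5.3 does not list such a rate as an output; it is implied by the dichotomy. The 5% to 25% range is an assumption.

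**Conclusion.** The label in SAP 5.5.3 conflicts with the protocol's own scale at one score, mRS 3. The 0–3 model is valid for its split, but its odds ratio should not be described as an effect on independence. Independence as labelled exceeds the mRS 0–2 proportion by exactly each arm's share at mRS 3, which the documents do not give. If the cut is also applied at baseline, the shift summary hides moves from 0–2 to 3.

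The severity is minor. A reader might infer that the trial's efficacy conclusion is at risk. It is not: mRS is an additional endpoint outside the primary and secondary testing hierarchy in SAP 5.1.1, and the primary and secondary conclusions do not depend on it. The conclusion assumes that readers will take functional independence to mean needing no help, which is how Appendix D separates score 2 from score 3.

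**What to change.** In SAP 5.5.3:

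1. Rename the existing category *mRS 0–3 (able to walk without assistance)* and keep its logistic model as specified.
2. Define functional independence as mRS 0–2, and state that the definition applies at both baseline and Day 30.
3. Base the shift table on that definition.
4. Report the 0–2 outcome by arm, using the same logistic model, as a supplementary analysis.

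The protocol gives no cut-point for the dichotomous analysis, so its text does not conflict with this change. The cost is a wording edit, one extra model and one table from data already collected, with no effect on alpha. The downside is a lower reported independence rate, by exactly each arm's mRS 3 share, and a second mRS odds ratio that must be presented as supplementary.
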